### 4.2.3. Main Analytical Approach

#### Progression-Free-Survival (PFS)

The non-parametric Kaplan-Meier method will be used to estimate the survival curves for PFS. Kaplan-Meier plots of PFS will be presented by treatment arm. Kaplan-Meier estimates for the median PFS, the first and third quartiles, and 6-month PFS rate will be presented, along with 95% CIs. CIs for quartiles will be estimated using Brookmeyer-Crowley method [Brookmeyer, 1982]. The treatment difference in PFS will be compared by the stratified log-rank test at one-sided alpha level of 0.025. The stratified log-rank test (stratified by randomization factors) will only be performed for the primary analysis of primary estimand of PFS (i.e. based on investigator-assessed response and primary event and censoring rules) based on ITT Analysis Set.

Hazard ratio (HR) and its corresponding 95% CI will be estimated from Cox proportional hazard model stratified by randomization factors with treatment arm as the sole explanatory variable. The Cox models will be fitted using SAS PROC PHREG with the Efron method to control for ties.

Hazard ratio (HR) and its corresponding 95% CI will also be estimated from unstratified Cox proportional hazard model with treatment arm as the sole explanatory variable. The Cox models will be fitted using SAS PROC PHREG with the Efron method to control for ties.

Stratification factors entered for randomization will be used in the primary analysis. If there is any mis-stratification, supplementary analyses will be performed using the stratification data based on the clinical database.

## Statistical Methodology Specification

Endpoint / Variables

 
PFS
 

Model Specification

 
PFS will be analyzed across treatment arms using Kaplan-Meier analysis (PROC LIFETEST).
 
95% Confidence intervals will be estimated using the Brookmeyer-Crowley method [Brookmeyer, 1982].
 
The treatment difference in PFS will be tested by the stratified log-rank test.
 
A stratified Cox proportional hazard model with Efron's method of tie handling and treatment arm as the sole explanatory variable will be used to assess the magnitude of the treatment difference (i.e., the hazard ratio) in PFS between the treatment arms.
 

Model Checking & Diagnostics

 
The proportional hazards assumption will be assessed using the following methods: 
 
Kaplan-Meier plot by treatment arm
 
Plot of log(time) against log(-log(survival)) by treatment arm
 
Plot of Schoenfeld residuals for treatment
 
Evaluation of time-dependency of treatment effect by adding an interaction term of treatment and time in the Cox model. If the interaction term is significant (<math>p < [0.10]</math>), it is considered that the proportional hazards assumption is violated.
 
 
 
If one or more of the procedures above demonstrates clear violation of the proportional hazards assumption in PFS, it is considered the proportional hazards assumption does not hold. Hazard ratio and corresponding 95% CI estimated from the Cox model will still be reported.
 
More details for handling possible non-proportional hazards effect are provided in Section 4.2.4.1.
 

Model Results Presentation

 
Kaplan-Meier estimates for the median PFS and the first and third quartiles will be presented, along with 95% CIs.
 
The p-value from the stratified log-rank test will be reported.
 
Hazard ratio and corresponding 95% confidence interval from the Cox model will be reported.
 

#### 4.2.4. Sensitivity analyses

##### 4.2.4.1. Non-Proportional Hazards Effect

If there is possible non-proportional hazards effect in PFS, the Restricted Mean Survival Time (RMST) method [Uno, 2015] may be conducted as appropriate, while the hazard ratio (HR) and its corresponding 95% CI based on Cox proportional hazard model will still be reported.

##### ***Restricted Mean Survival Time (RMST)***

RMST method may be conducted to account for the possible non-proportional hazards effect. The RMST is the expected survival time restricted to a specific time horizon  $t^*$ . The cutoff  $t^*$  for determining the RMST will be the smallest value among the largest observed time across study interventions.

**Statistical Methodology Specification**

Endpoint / Variables

 
PFS
 

Model Specification

 
Additional analysis based on RMST will be conducted if the proportional hazard assumption does not hold.
 
RMST at <math>t^*</math> will be estimated from the Kaplan-Meier curve for each treatment arm:                     <math display="block">\mu_{t^*} = \int_0^{t^*} S(t) dt</math> 
 
RMST difference at <math>t^*</math> (<math>\hat{\Delta}_{t^*}</math>) between treatment arms will be estimated as:                     <math display="block">\hat{\Delta}_{t^*} = \int_0^{t^*} [\hat{S}_T(t) - \hat{S}_C(t)] dt</math> 
 
95% CI for RMST difference and the p-value will be estimated using the following formula under normal approximation (Klein, 2005):                     <math display="block">Var(\hat{\Delta}_{t^*}) = V[\hat{\mu}_{t^*}(T)] + V[\hat{\mu}_{t^*}(C)]</math> <math display="block">V[\hat{\mu}_{t^*}] = \sum_{i=1}^D \left[ \int_{t_i}^{t^*} \hat{S}(t) dt \right]^2 \frac{d_i}{Y_i(Y_i - d_i)}</math>                     where <math>d_i</math> is the number of events and <math>Y_i</math> is number of participants at risk at <math>t_i</math>.                 
 

SAS Procedure

 
SAS/STAT 15.1 will be used for the statistical analysis.
 
Proc LIFETEST will be used with RMST option in order to obtain the RMST in both the treatment groups.
 
Proc RMSTREG will be used to obtain the RMST difference between the groups and corresponding 95% CI. The option link=linear will be specified. “Mean Plot” with “CLBAND” option will be used to generate the RMST plot with confidence bands.
 

Model Results Presentation

 
If the proportional hazard assumption does not hold, the p-value based on the RMST test will also be reported in addition to the stratified log-rank test p-value.
 
RMST difference at <math>t^*</math>, and the corresponding 95% confidence interval will be presented.
 
A plot of RMST up to <math>t^*</math> and the corresponding 95% simultaneous confidence bands will be generated.
 

**4.2.4.2. Sensitivity Analysis of Primary Estimand of PFS on Independent Review Committee (IRC) assessed response**

If a review by IRC is conducted on all the disease assessments, a sensitivity analysis of the primary estimand of PFS (i.e. handling of intercurrent events based on primary event and censoring rules) will be conducted based on the IRC-assessed response. The sensitivity analyses will only use the Kaplan-Meier estimates, Cox proportional hazards model stratified by randomization factors described in Section 4.2.3. This analysis won't be available at the time of Study Analysis Complete (SAC) but will only be conducted

after the full IRC review is finished. If a review by IRC is conducted only on a randomly selected subjects, statistical analyses specified in the IRC audit plan on the IRC- assessed response will be conducted. This analysis won't be available at the time of SAC but will only be conducted after the IRC review on the randomly selected subjects is finished.

#### **4.2.5. Supplementary Analyses**

##### **4.2.5.1. Analysis of Supplementary Estimand of PFS**

Additional analyses of the supplementary estimands 1&2 (i.e. handling of intercurrent events based on alternative event and censoring rules 1&2) of PFS will be conducted based on investigator-assessed response.

These additional analyses will only use the Kaplan-Meier estimates and Cox proportional hazards model stratified by randomization factors described in Section [4.2.3](#).

##### **4.2.5.2. Analysis of PFS based on mITT Analysis Set**

The following sets of analyses will also be conducted based on the mITT analysis set using investigator-assessed response:

- [1]. Primary analysis of primary estimand ( investigator-assessed response + primary censoring rules);
- [2]. Primary analysis of supplementary estimand 1 ( investigator-assessed response + alternative censoring rules 1);
- [3]. Primary analysis of supplementary estimand 2 ( investigator-assessed response + alternative censoring rules 2);

The analytical approach for each analysis above is: Kaplan-Meier estimates and Cox proportional hazards model stratified by randomization factors as described in Section [4.2.3](#).

##### **4.2.5.3. Analysis of PFS based on Stratification Data from the Clinical Database**

If there is any mis-stratification for stratification factors entered for randomization, the following supplementary analysis will be performed using the stratification data based on the clinical database.

- [1]. Primary analysis of primary estimand ( investigator-assessed response + primary censoring rules);

The analytical approach is: Cox proportional hazards model stratified by randomization factors (based on data from the clinical database).

### **4.3. Secondary Endpoint(s) Analyses**

#### **4.3.1. Key secondary endpoint**

Key secondary endpoints are those secondary endpoints for which a label claim is pursued as part of the confirmatory hypotheses for which the type 1 error is controlled (multiplicity adjustment). The analyses of OS will be based on the ITT Analysis Set, unless otherwise specified. In addition, pending on maturity of data, the survival probability at 6, 12 and 18 months with 95% CI will be estimated using Kaplan-Meier method.

##### **4.3.1.1. Definition of endpoint**

The key secondary endpoint in this study is Overall Survival (OS), defined as the interval of time from randomization to the date of death due to any cause. Participants who are alive will be censored at the last known date of last contact. Participants without documented death will be censored at last known alive date. The last date will be determined by the maximum collection/assessment date from among selected data domains within the clinical database; details will be provided in a separate Output and Programming Specification (OPS) document. When calculating overall survival, all deaths following subsequent anti-cancer therapy will be included. This is the primary estimand of OS, and there is no supplementary estimand of OS.

##### **4.3.1.2. Main analytical approach**

Refer to Section 4.2.3 (i.e. Kaplan-Meier estimates, stratified log-rank test, Cox proportional hazards model stratified by randomization factors, and examination of non-proportional hazards effect).

##### **4.3.1.3. Sensitivity analyses**

The analyses in this section may only be conducted at the 2nd interim and final analysis for OS when OS data is more mature.

If there is possible non-proportional hazards effect, refer to Section 4.2.4.1 for RMST method.

To obtain a less biased estimate of treatment effect, an IPCW method will be performed for OS adjusting for the post study therapy [Watkins, 2013]. To compensate the impact of switching to another therapy, patients with similar characteristics to those patients that switched treatment are obtained and assigned a higher weight to the patient that stayed on treatment and a lower weight to the patients receiving post study therapy. To calculate these weights, the likelihood of remaining uncensored will be estimated by logistic regression. Specifically, two logistic regression models, one using only baseline covariates and other using both baseline and time dependent covariates will be performed. The coefficient between these two estimated probabilities of switching is going to give the assigned weights. Subsequently, patients who switched will have a lower weight than patients that did not.

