1.1.2. Estimands

Table 1 Estimands

Objective	Estimand Category	Estimand			Population Level Summary Measure
		Variable/Endpoint	Analysis Set	Intercurrent Event Strategy	
Primary Objective: To demonstrate the superiority of belantamab mafodotin compared to pomalidomide plus low dose dexamethasone (pom/dex) in PFS in participants with relapsed/refractory multiple myeloma (RRMM) [1]	Primary	PFS	ITT	
 
• Disease assessments between scheduled visits: treatment policy
 
• New anti-cancer therapy: while on treatment
 
• Extended loss to follow-up: while on treatment
 
• Treatment discontinuation: treatment policy
 
• Death: composite
 
	Hazard ratio for belantamab mafodotin vs pom/dex
	Supplementary 1	PFS	ITT	
 
• Disease assessments between scheduled visits: hypothetical
 
• New anti-cancer therapy: while on treatment
 
• Extended loss to follow-up: while on treatment
 
• Treatment discontinuation: treatment policy
 
• Death: composite
 
	Hazard ratio for belantamab mafodotin vs pom/dex
	Supplementary 2	PFS	ITT	
 
• Disease assessments between scheduled visits: treatment policy
 
• New anti-cancer therapy: composite
 
• Extended loss to follow-up: treatment policy
 
• Treatment discontinuation: composite
 
• Death: composite
 
	Hazard ratio for belantamab mafodotin vs pom/dex
Key Secondary Objective: To demonstrate the superiority of belantamab mafodotin compared to pomalidomide plus low dose dexamethasone (pom/dex) in OS in participants with relapsed/refractory multiple myeloma (RRMM) [1]	Primary	OS	ITT	Survival benefit regardless of subsequent anticancer therapies or treatment compliance 
 
• New anti-cancer therapy: treatment policy
 
• Treatment discontinuation: treatment policy
 
	Hazard ratio for belantamab mafodotin vs pom/dex

Objective	Estimand Category	Estimand			Population Level Summary Measure
		Variable/Endpoint	Analysis Set	Intercurrent Event Strategy	

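### SAP Section 4.3.1.3 is inconsistent about which probabilities form the OS IPCW weights, and about whether switchers are censored or only down-weighted

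*SAP*

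**What the plan says.** SAP Section 4.3.1.3 plans one analysis that deals with therapy started after study treatment: "To obtain a less biased estimate of treatment effect, an IPCW method will be performed for OS adjusting for the post study therapy". It describes the weights in four steps.

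- **Aim.** Patients who resemble switchers are to be identified and "assigned a higher weight to the patient that stayed on treatment and a lower weight to the patients receiving post study therapy".
- **Quantity modelled.** "the likelihood of remaining uncensored will be estimated by logistic regression", using two models: one with baseline covariates only, and one that adds time-dependent covariates.
- **Weight.** "The coefficient between these two estimated probabilities of switching is going to give the assigned weights".
- **Consequence.** "Subsequently, patients who switched will have a lower weight than patients that did not".

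No sentence in the section says that follow-up is censored when new therapy starts, which model supplies the numerator, or that interval probabilities are multiplied over time. The section's analyses may be confined to the second interim and the final OS analysis.

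For the primary OS analysis, Section 4.3.1.1 says: "When calculating overall survival, all deaths following subsequent anti-cancer therapy will be included". Table 1 in Section 1.1.2 describes that estimand as "Survival benefit regardless of subsequent anticancer therapies or treatment compliance". Section 4.3.1.2 points to Section 4.2.3 for the main methods, including the "Cox proportional hazards model stratified by randomization factors, and examination of non-proportional hazards effect".

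**The concern.** IPCW censors each patient at the switch. It then re-weights those still unswitched by the inverse of their probability of remaining so, so that they also stand in for similar patients who have been censored. Section 4.3.1.3 departs from this in two ways.

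1. The probability it says is modelled (remaining uncensored) and the one it says forms the weight (switching) are complements. A ratio of one is not the ratio of the other. The word *coefficient* presumably means quotient, but its order is not given.
2. Saying that switchers carry a lower weight suggests that they stay in the weighted analysis. Under IPCW they contribute person-time up to the switch and nothing afterwards.

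A programmer who follows the words could therefore build weights that are not IPCW weights. If the point is settled only after OS data are available, the choice of weighting would be made with results in view.

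**Working it through.** The SAP gives no figure for this analysis, so there is none to reproduce. The check is algebraic. The probabilities below are assumptions, because the SAP states no switching rates and no interval length.

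**Definitions.** For one patient in one interval:

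- p0 = probability of switching from the baseline-covariate model
- p1 = probability of switching from the model with baseline and time-dependent covariates

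A stayer who resembles switchers has p1 > p0.

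**Weights compared (one interval).**

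- Stabilised IPCW weight: (1 − p0)/(1 − p1), multiplied over intervals up to the switch
- Literal text, first order: p0/p1
- Literal text, inverse order: p1/p0

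**Direction.** If p1 > p0, then (1 − p0)/(1 − p1) > 1 and p0/p1 < 1. The first order therefore lowers the weight of exactly those stayers whom the section wants to weight up. This holds for any values. The inverse order p1/p0 exceeds 1, so its direction is right.

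**Size.** When does each ratio equal the IPCW weight?

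- p0/p1 = (1 − p0)/(1 − p1) requires p0(1 − p1) = p1(1 − p0), that is p0 = p1.
- p1/p0 = (1 − p0)/(1 − p1) requires p1(1 − p1) = p0(1 − p0), that is (p1 − p0)(1 − p0 − p1) = 0. So p0 = p1 or p0 + p1 = 1.

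**Numbers (all inputs assumed).**

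| p0 | p1 | IPCW (1 − p0)/(1 − p1) | p0/p1 | p1/p0 |
|---|---|---|---|---|
| 0.05 | 0.075 | 0.950/0.925 = 1.03 | 0.67 | 1.50 |
| 0.10 | 0.30 | 0.90/0.70 = 1.29 | 0.33 | 3.00 |
| 0.30 | 0.60 | 0.70/0.40 = 1.75 | 0.50 | 2.00 |
| 0.30 | 0.10 | 0.70/0.90 = 0.78 | 3.00 | 0.33 |
| 0.40 | 0.60 | 0.60/0.40 = 1.50 | 0.67 | 1.50 |

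The fourth row is a stayer unlike switchers. The IPCW weight falls below 1, but p0/p1 triples that patient's weight. The last row is the special case p0 + p1 = 1, where p1/p0 coincides with the IPCW weight.

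**Switchers.** The named method and the phrase about remaining uncensored both imply censoring at the switch. The two statements about a lower weight imply retention. The section does not choose between them.

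**The case against.** The best defence is that the intent is recoverable. The pair of probabilities in the weight sentence refers back to the two models just described, and those were introduced as models for remaining uncensored. On that reading *of switching* is a loose label, and baseline model over full model is the correct ratio. The method's name implies censoring, and the SAP version history (amendment 1, item 11) describes the addition as an OS analysis that censors patients at subsequent therapy. This largely stands as evidence of intent. It does not remove the inconsistency: the operative text still names the complementary probability, leaves the order open and twice gives switchers a lower weight.

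Three stronger readings are tempting, but the document does not support them.

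- *The plan definitely prescribes a wrong weight.* The text is wrong if taken literally, but the charitable reading is available. Inconsistent is the accurate description.
- *Section 4.3.1.1 conflicts with the analysis because it counts deaths after subsequent therapy.* That rule defines the primary OS estimand. A sensitivity analysis that adjusts for later therapy departs from it by design.
- *Either literal ratio is always worse than no weighting.* This depends on the assumed rates. Suppose 25% of patients have p1 = 0.60 and overall p0 = 0.40, so the rest have (0.40 − 0.25 × 0.60)/0.75 = 0.333. After one interval the high-risk type makes up 0.10/0.60 = 16.7% of unweighted stayers. Weights p1/p0 of 1.50 and 0.833 give 0.150/(0.150 + 0.417) = 26.5%, close to the 25% target.

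**Conclusion.** The point holds as an internal inconsistency that should be corrected. Taken literally, one order of the ratio reverses the intended weighting for any p1 ≠ p0. The other matches the IPCW weight only if p0 = p1 or p0 + p1 = 1. At the assumed p0 = 0.10 and p1 = 0.30, a stayer would get 0.33 or 3.00 instead of 1.29. The reversal is algebraic, while the sizes rest on assumed switching probabilities.

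The reach is narrow. This is a non-confirmatory sensitivity analysis of the key secondary endpoint, which may be run only at the later OS looks. The stratified log-rank test, the OS alpha, the stopping boundaries and the power are untouched. A reader might infer that the reported OS hazard ratio would be distorted. The SAP gives nothing from which to derive such an effect, and none is claimed.

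**What to change.** Amend Section 4.3.1.3 as follows.

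1. State that, for this analysis, OS follow-up is censored at the start of the first new anti-cancer therapy.
2. Define the time-varying weight as the cumulative product over intervals of P(remaining unswitched | baseline covariates) / P(remaining unswitched | baseline and time-dependent covariates).
3. Apply it to person-time before the switch in the stratified Cox model of Section 4.2.3, with a robust variance.
4. Delete the wording on probabilities of switching and on a lower weight for switchers.

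Both planned logistic models are kept. The cost is a few sentences and slightly more programming, with no change to the sample size or the confirmatory OS testing.

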#### 4.3.1.4. Supplementary Analyses

##### ***Analysis of OS based on mITT Analysis Set***

Analyses of OS will also be conducted based on the mITT analysis set. The analytical approach for each analysis above is Kaplan-Meier estimates and Cox proportional hazards model stratified by randomization factors as described in Section 4.2.3.

##### ***Analysis of OS based on Stratification Data from the Clinical Database***

If there is any mis-stratification for stratification factors entered for randomization, the following supplementary analysis will be performed using the stratification data based on the clinical database. The analytical approach is Cox proportional hazards model stratified by randomization factors (based on data from the clinical database).

#### 4.3.2. Supportive secondary endpoint(s)

##### 4.3.2.1. Supportive Secondary Efficacy Endpoint(s)

Primary analysis of supportive secondary efficacy endpoints will be based on investigator-assessed response. Analyses of supportive secondary efficacy endpoints will be based on the ITT Analysis Set, unless otherwise specified.

##### ***Definition of Endpoint(s)***

At final PFS/OS analysis, the analyses for the following supportive secondary efficacy endpoints will be conducted:

- **Overall response rate (ORR)**, is defined as the percentage of participants with a confirmed PR or better (i.e., PR, VGPR, CR, and sCR).
- **Clinical benefit rate (CBR)**, is defined as the percentage of participants with a confirmed minimal response (MR) or better.  
ORR and CBR will be analyzed based on the confirmed responses, which will be derived based on the algorithm specified in Table 3. Only the assessments from the start of treatment up to the earlier of confirmed disease progression or the start of new anti-cancer therapy will be considered. Only new systemic anti-cancer drugs taken are considered as anti-cancer therapy (radiotherapy and surgeries are not considered as systemic anti-cancer therapy for the purpose of this analysis). Participants with only assessments of Not Evaluable or missing response will be treated as non-responders; i.e. they will be included in the denominator when calculating the percentage.
- **Duration of response (DoR)** is defined as the time from first documented evidence of PR or better until the earliest date of disease progression (PD), or death due to any cause among participants who achieve a response (i.e., confirmed PR or better). Responders without disease progression will be censored at the censoring time point for PFS.
- **Time to response (TTR)** is defined as the time between the date of randomization and the first documented evidence of response (PR or better), among participants who achieve a response (i.e., confirmed PR or better).

- **Time to progression (TTP)** is defined as the time from randomization until the earliest date of PD, or death due to PD. Determination of dates of TTP event and dates for censoring are described in the [Table 4](#).
- **Minimal Residual Disease (MRD) Negativity Rate**, is defined as: the percentage of participants who are MRD negative by Next Generation Sequencing (NGS).

